i) neurosurgery ii) cardiothoracic iii) spinal injuries iv)specialised paeds v)neonatal intensive vi) Medium secure units/challenging behav. vii) renal viii) rehabilitation ix) genetics	i)-v) are services for relatively rare conditions, in which one would expect either cost per case contracts plus perhaps a move to more co-ordinated purchasing with the HA or other TPPs As above, but scope for maintenance contracts (per patient year) Expect TPPs to purchase more, either separately or as part of packages Small but growing. Expect cost per test contracts plus growth of TPP site clinical genetics
Palliative care	Shift to more patient-oriented care Shift from acute hospital spells to community services Contracts for packages of care or whole services Development of respite care
Mental illness	Shift in balance of drug/inpatient treatment (fewer inpatient spells and inpatient days, change in drugs such as SSRIs, depending on evolving literature) Increase in use of distant NHS and private beds in emergencies if no NHS bed available locally Change in emphasis to primary care mental health services with knock-on effects on providers
Community services	More closely targeted & monitored Contracts for staff inputs/whole services
Health promotion	Shift to interventions with known cost- effectiveness Contracts for staff inputs/whole services

Method

Routine NHS data from England and Scotland will be used to describe changes in the seven services at all the TPP sites before and after TP. There will be two comparators: patients of SFH practices in the relevant district and all the patients whether of SFH or non-FH practices of the district as purchaser. The impact of TP on A&E service use will be studied separately because of the lack of activity data available routinely. A feasibility study has been undertaken which is the subject of a

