separate proposal and contract (not included in this proposal). The scope for using routine NHS data to monitor changes in the seven services discussed above is summarised in Table 5.2, which suggests that the routine data, notably the Hospital Episode Statistics (HES) in England, would provide valuable information in relation to three services: emergency admissions, maternity and regional specialties. HES can provide up-to-date data on all inpatient and day case episodes, along with demographic and clinical data. National HES data for 1993/4 along with regional data for 1994/5 and 1995/6 would be used to set baseline levels. Regional data would be used to monitor changes in each of these services. Members of the team have considerable expertise in such analysis at both regional and national level and are confident about being able to negotiate national HES through the National Casemix Office, as has been the case for other projects. (One of the team -[name] - works part time for the National Casemix Office.) Local HES data would be obtained via the TPP site/DHA. Preliminary consultations with Scottish Home and Health Department statisticians indicates that Scottish routine data are highly compatible with English HES and of higher quality. There should be no great difficulty producing an Anglo-Scottish analysis of activity trends. Routine data would have to be supplemented by collection of data at TPP level on use of non-NHS services. This could be obtained from TPP practice software for those sites reporting use of non-NHS services during the fieldwork described in the previous main section.

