Routine data, specifically HES, Community Korner and PACT data, would be of more limited use in the other four services, for which developments in information for contracting might also be expected (see Table 5.2). Both palliative care and mental health, which have growing elements of community and domiciliary care, are only partially captured by routine data, with its emphasis on NHS inpatient activity, leaving gaps regarding community service contacts with patients linked to diseases or to GPs. Although total community health service contacts are recorded, these cannot be linked to specific client groups or patients (the advent of the new computable NHS number will change this - the scope for its use by TPPs will be explored). Data on activity in both community health services and on health promotion are so weak that TPPs may choose to contract on the basis of staff inputs and/or clinics and sessions. For each of these services, routine NHS data would be supplemented by data from each TPP site, depending on how these data are specified by each in their contracting and monitoring arrangements.

Table 5.2
Routine data by topic and adequacy to detect changes in patterns of services

Service	Routine Data	Adequacy
Emergency Admissions	HES/SMR1	OK (all below omit private sector)
Maternity	HES/SMR1	ditto
Regional specialties	HES/SMR1	ditto
Palliative care	HES/SMR1 re NHS inpatients only	missing community service contacts to terminally ill
Mental illness	HES/SMR1 re NHS inpatients only, CPN contacts, PACT	missing community service contacts to mentally ill
Community services	contacts Staff numbers	no linkage to client groups
Health promotion	Clinics Staff numbers	ditto

HES diagnostic data has strict limitations. It is likely that it will only be possible to analyse trends in major diagnostic grouping or by ICD chapters.

Ideally, the analysis of routine data (eg HES/SMR1) would be undertaken for 1993/94, 1994/95, 1995/96 and 1996/97 as soon as possible after the end of March 1997 in order to contribute these analyses to the final report due at the end of September 1997. Unfortunately, there is likely to be a considerable lag in the availability of routine data. It could be October before a complete 1996/97 HES/SMR1 data set is available. Thus, it may not be possible to report on the changes in activity rates before the end of 1997.

Additional data to validate and interpret routine data

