TPPs may wish to contract for **renal services** on the basis of maintenance contracts as some DHAs have done as a means of avoiding the problems associated with contracting on the basis of a mixture of FCEs and outpatient attendances.

As rehabilitation is a service with many more potential clients, a different pattern may emerge. Stroke provides a useful example, in that almost all admissions are emergency, and changes might be expected from TP, with a shift from long stay acute care to rehabilitation whether in hospital, community or at home. Nationally, around 10% of stroke patients stay in acute hospitals for long spells and account for around 60% of inpatient days. These might be expected to be shifted more rapidly either to their homes, with community service backup, or to nursing homes, depending on availability and finance. TPPs may well contract separately for rehabilitation inputs or specify them as part of inpatient stays. Other groups requiring rehabilitation include younger persons who have been seriously injured (such as head injuries). TPPs might spur local strategies to deal with rehabilitation in general.

Genetics is a small but growing services which includes clinical and lab services. Much depends on the advent of new tests which are proliferating. TPPs might be expected to develop overall strategies, perhaps in conjunction with DHAs. Alternatively, TPPs might contract individually on a cost per test basis with laboratories and provide the clinical genetics service, which is largely education and counselling, at TP level.

Palliative care

TP might be expected to lead to more patient-oriented palliative care. A rise in the proportion of deaths occurring at home might be expected given evidence on patients' preferences. A shift might also be expected from costly acute hospital spells to community services, with greater co-ordination of the range of inpatient, community and hospice services.

26 January 1996

Mental illness

TP might be expected to lead to a shift in the balance between drug and inpatient treatment as the costs of the latter become more obvious. Prescriptions of new costly psychiatric drugs such as the SSRIs might be expected to change, relative to both SFH controls and to the baseline year (see below section on prescribing). An increase might be expected in the use of distant NHS beds or private sector beds in emergencies if no NHS beds are available locally.

Community services

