A different perspective on the availability of services will also be sought from all the Provider units related to a sample of the Total Purchasing sites with and without a special interest in mental health and from GPMH sites. By means of telephone interviews with Clinical Directors followed where necessary by personal visits, the relative contributions of the different purchasing models to changes in the availability and configuration of services will be defined, comparing the start-up period with one year later.

Utilisation of services

Information about *utilisation* of services will be obtained from hospital in-patient episode databases, focusing on admission rates and length of stay for patients with diagnoses in ICD9 Chapter V who are registered with GPs in each Total Purchasing site, in GPMH practices, and also in each reference site. These data will be analysed for April 1995 to March 1996, and for April 1996 to March 1997. Information will be sought from the study sites about any action taken to reduce admissions and length of stay, e.g. the employment of nurses to visit the in-patient units to expedite discharge.

For out-patient referrals information will be sought from the relevant providers including practices and Community Mental Health Teams by means of available databases (including practice billing systems) and also through individual Community Psychiatric Nurse workload schedules in the sample of Total Purchasing, GPMH and reference sites selected for special study. This will depend on the availability of routine nursing data being available from existing sources. Reliable

outpatient information will be difficult to collect because of the wide variety of types of secondary mental health contact, and it will not be possible to determine how much out patient data will be collected until individual sites are visited. Changes in outpatient utilisation rates are not essential to this part of the study.

Needs assessment and information systems

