This part of the study will be carried out in collaboration with the economists involved in the Total Purchasing Evaluation Consortium ([name], York; [name], LSE; [name], Bristol; [name], Southampton). The aims of the economic aspects of this study are:

- * to examine service cost implications of any differences in service use by TP, GPMH sites and their comparators;
- * to explore the link between costs and outcomes.

Data will be collected on the NHS resource use by TP sites, GPMH sites and their comparators. Only direct costs will be considered, i.e. those that fall within the NHS or Social Services. Indirect costs (i.e. those incurred by users and informal carers) are beyond the scope of this study, given the resources available. The study will compare study sites to controls and will compare the initial position regarding services for mental health and illness at all study sites with the situation after the first year of operation.

Methods

Physical resource use

Data on the physical quantities of resources will be as far as possible collected prospectively as part of Study 1. Inpatient data including admission rates, length of stay and destination on discharge will be collected from HES data. For outpatient referrals and other services information will be sought through a combination of the Community Mental Health Team and individual Community Psychiatric Nurse workload schedules. Until individual sites are visited it will not be clear to what extent such data can feasibly be collected.

The evaluation of Total Purchasing includes assessment of transaction costs. It is not proposed to replicate this for GPMH sites, since contracting just for inpatient mental health services is unlikely to represent a long term purchasing model.

Unit costs

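### Private psychiatric beds, which TP may use more in emergencies, are missing from the NHS inpatient data, and Section 5.1 collects non-NHS use only at pilot sites

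*Protocol*

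**What the plan says.** **What TP is expected to do.** For mental illness, Protocol Table 5.1 lists "Increase in use of distant NHS and private beds in emergencies if no NHS bed available locally". Annexe 5 repeats it: "An increase might be expected in the use of distant NHS beds or private sector beds in emergencies if no NHS beds are available locally". The same cell of Table 5.1 also predicts "fewer inpatient spells and inpatient days, change in drugs such as SSRIs".

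**What the routine data cover.** The adequacy column of Table 5.2 opens with "OK (all below omit private sector", and the mental illness row reads "HES/SMR1 re NHS inpatients only, CPN contacts, PACT".

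**How the gap is filled in Section 5.1.** The Method paragraphs say: "Routine data would have to be supplemented by collection of data at TPP level on use of non-NHS services". The suggested source is pilot practice software, at those sites that report non-NHS use during fieldwork. The comparators in that section are patients of standard fundholding (SFH) practices in the district and all patients of the district as purchaser. No equivalent collection is described for them.

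**What the mental-health proposal uses.** Study 1 says that information on utilisation of "services will be obtained from hospital in-patient episode databases, focusing on admission rates and length of stay", for TP sites, practices in the mental health inpatient extension of fundholding (GPMH) and reference sites, over 1995/96 and 1996/97. Its sample size paragraph takes admission rates from National Casemix Office routine data. Study 4 says: "Inpatient data including admission rates, length of stay and destination on discharge will be collected from HES data". Study 4 counts as direct any cost falling on the NHS or social services, so an NHS-funded private placement is within its scope.

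**The concern.** The plan names an event that it expects TP to cause and then measures admissions with a source that cannot see it. A patient moved from an NHS bed to a private bed and a patient who was never admitted look the same in NHS inpatient data. The second is the reduction the evaluation hopes to detect.

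Two separate problems follow, in two components.

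1. **Section 5.1.** Non-NHS use is collected on the pilot side only. If it is added to pilot activity, the pilot sites are counted on NHS plus private care and the comparators on NHS care alone. A true TP reduction would then be understated.
2. **Mental-health Studies 1 and 4.** The source is the same in every arm and private care is missing from all of them. If private placements rise more at TP sites than elsewhere, TP admissions and inpatient resource use appear to fall. A TP reduction would then be overstated, or created where there is none.

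The two errors run in opposite directions, so the two components could disagree about psychiatric admissions for reasons of data capture alone.

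**Working it through.** **Inputs from the documents** (mental-health proposal, Study 1, sample size and power): psychiatric admission rates of 0.8 and 0.4 per 1000 per year; detectable rates of 0.55 and 0.3; 80% power; 5% significance.

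**Input not in the documents:** the private share of psychiatric admissions. Let f be the share in TP patients and g the share in comparators. Both are assumptions, shown over a range.

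**Step 1. Reproduce the plan's figure.**
- 1 − 0.55/0.8 = 31.25%
- 1 − 0.3/0.4 = 25%

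Both agree with the stated range of a quarter to a third. The 80% power cannot be checked, because neither the between-practice variation nor the number of units analysed is given.

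**Step 2. NHS data only in both groups (Studies 1 and 4).** With equal true total rates, the observed rate ratio is (1 − f)/(1 − g).

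| f | g | Observed ratio |
|---|---|---|
| 5% | 0 | 0.95 |
| 10% | 0 | 0.90 |
| 15% | 0 | 0.85 |
| 25% | 0 | 0.75 |
| 10% | 5% | 0.947 |
| 15% | 5% | 0.895 |
| 5% | 5% | 1.00 |

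With g = 0, the spurious fall equals the private share. To imitate the whole detectable effect, the share would have to be 25% in the lower-rate county (0.4 × 0.75 = 0.30) or 31.25% in the higher-rate county (0.8 × 0.6875 = 0.55). With f = g there is no bias. In the before-and-after comparison, what matters is whether the proportion of admissions still in NHS beds changes by a different factor in the two groups.

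**Step 3. What this does to the test.** The standard error of the log rate ratio implied by the stated design, taking the test as two-sided, is ln(0.8/0.55)/(1.96 + 0.84) = 0.134 and ln(0.4/0.3)/(1.96 + 0.84) = 0.103. With no true change and g = 0, the chance of a significant result, against a nominal 5%, is:

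| f | 0.8 county | 0.4 county |
|---|---|---|
| 5% | 7% | 8% |
| 10% | 12% | 18% |
| 15% | 23% | 35% |

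**Step 4. A complete supplement on the pilot side only (Section 5.1, if the counts are added).** The observed ratio is the true ratio divided by (1 − g). With no true change it is 1.02, 1.05 and 1.11 for g = 2%, 5% and 10%. At g = 5%, a true 31.25% reduction appears as 1 − 0.6875/0.95 = 27.6%, and a true 25% reduction as 1 − 0.75/0.95 = 21.1%.

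**Step 5. The same capture in both groups.** The observed ratio equals the true ratio, and both artefacts disappear.

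**The case against.** **The mental-health study treats all arms alike.** A reader might infer that it too suffers from one-sided data collection. The documents do not support that: the pilot-only supplement belongs to Section 5.1, and Studies 1 and 4 draw on the same NHS source for TP, GPMH and reference patients. Reference practices are also to share the main mental-health provider, so a local bed shortage would press on both groups. This stands, and it is why problem 2 needs a differential change in private use. It does not remove the problem, because the hypothesis presents the rise in private use as an effect of TP.

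**Section 5.1 does not say the supplement will be added to pilot rates in the between-group comparison.** This is correct. The understatement in Step 4 is conditional on that use of the data.

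**A reader might infer that costs as a whole come from HES.** They do not. HES gives inpatient quantities. Unit costs come from authority financial returns (Section 5.2), or from published unit costs and some local contract prices (Study 4). A missing quantity still carries through to cost.

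**Other comparator-side sources exist.** Health commissions are approached to validate routine data (Section 5.1), host-authority mental-health contracts are obtained (Section 5.3), and Study 2 asks about unplanned admissions. None is set up to count comparators' private admissions.

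**The limitation is partly disclosed.** Section 5.1 does not list mental illness among the three services for which HES is valuable. The powered admission comparison in Study 1 nevertheless rests on routine inpatient data.

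**The hypothesis is limited.** It applies only where no local NHS bed is free, and part of it concerns distant NHS beds, which are not private. This stands, and it argues for caution about size.

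**Conclusion.** The point holds as two separate problems. In Section 5.1 the collection of non-NHS use is one-sided and would understate a TP reduction if merged into pilot activity. In mental-health Studies 1 and 4 the collection is even-handed but blind to private beds, so a rise in private placements specific to TP would read as a fall in admissions and inpatient resource use.

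The size cannot be fixed from the documents. The falls of 5% to 25% assume no true change and no private use at baseline or among comparators; they shrink as comparator use rises and vanish when the shares move together. A reader might take a 25% share as a likely value because it matches the detectable effect in the lower-rate county. It is only the value at which the artefact would equal that effect, and nothing in the protocol suggests that private use would be that high. At an assumed 10% share confined to TP sites, the chance of a false signal is 12% to 18%. That is enough to justify a modest change to data collection, but it does not show that the comparison is invalid.

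**What to change.** Obtain counts, dates and prices of NHS-funded non-NHS psychiatric admissions for TP, GPMH and reference or district patients, in each year, from whichever body paid:

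- the health authority, for all groups before budgets went live and wherever a service was left to it;
- the TP or GPMH site afterwards.

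Following the payer matters. Section 2 says most sites start purchasing only in April 1996, and the interview guides allow for services left with the authority. A request to sites alone would miss baseline placements.

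Add these admissions to the NHS data in all arms of Studies 1 and 4, and report private placements as a separate result, since Table 5.1 predicts them.

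Where they cannot be obtained for comparators, restrict every between-group comparison, in Section 5.1 and in the mental-health study, to NHS activity. Report the pilot-site supplement separately, and state that a fall in NHS admissions cannot be read as a fall in total admissions or cost. This fallback makes the comparison even-handed but still does not capture private use, so the caveat must travel with the result.

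The cost is one further data request to authorities already asked for contracts and financial returns. Some may supply only district-level counts, which would not support the practice-level analysis.
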